### 2. Treatment index

#### **Primary Objective -- New users of DEX (DEX+) versus matched non-users of CSI (CSI-):**

From the patients who enter the cohort, new users of DEX between the admission date (*Day 0*) and 1 day prior to discharge date (*Day D-1*) or a maximum period of 21 days after admission (*Day 21*) will be selected. Greater than 80% of the patients who initiated DEX did so within 1 or 2 days of their hospitalization. A sensitivity analysis (SA2) will be conducted to explore initiation dates further. For each new user of DEX, at least 1 patient who has not (yet) used any CSI as of the DEX patient's index date or within the 90-day washout period prior matched on the

criteria defined in Table 2 below will be randomly risk-set sampled (RSS). DEX+ versus CSI-matching ratios of 1:1, 1:2, 1:3, and 1:4 will be considered to select up to 4 non-user referent patients for each exposed, and the ideal ratio will be selected based on the diagnostic criteria [defined below in section *VI.B. Diagnostic phase and checklist*].

RSS matching allows us to proxy the ‘standard of care’ by randomly selecting 1 or more patients who have not initiated DEX from the risk set of patients who are eligible for initiating DEX at the same time [*Li 2001*]. Since the COVID-19 pandemic and treatment of patients with COVID-19 is rapidly changing over time, there is much potential for calendar-time bias. Furthermore, patients prescribed DEX may appreciably differ from those not prescribed DEX. Employing an RSS that matches DEX users and non-users on the date of DEX treatment (in the users) and time since admission will minimize the potential for this bias. Cohort entry month will also be included in the propensity score (PS) calculation to further adjust for time-related biases. Geographic region was considered for the RSS matching criteria. However, during our data explorations, the comparison of baseline balance showed that matching without region yielded better baseline balance than matching with region. Therefore, we removed region from the RSS matching. However, given known regional differences, we still account for region in our propensity score model.

The *treatment index date* (Day T) for patients who are users and for the matched non-user referent patients will be defined by the index date of the matched users.

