### 3. Exclusion criteria

Patients who meet any of the following criteria will be excluded from the study cohort:

- No interaction with the healthcare system (medical encounter) in the 183 days prior to and including hospital admission (*Day -183 to Day 0*) to minimize the potential for misclassification of baseline covariates and/or new use
- No age or sex recorded in the 183 days prior to and including hospital admission (*Day -183 to Day 0*) as required for matching
- No geographic region recorded in 183 days prior to and including hospital admission (*Day -183 to Day 0*) as necessary to adjust for regional variation
- Any recorded use of any CSI (dispensing or remaining supply) in the 90-day washout prior to the treatment index date (*Day T-90 to Day T-1*) to satisfy new use definition
- Any record of a COVID-19 vaccine recorded on or any time prior to the treatment index date given that these patients are assumed to be selectively different (*Day S to Day T*)

The following will be evaluated (one at a time) in sensitivity analyses in order to tighten or loosen some of the exclusion criteria:

- Two sensitivity analyses will restrict the study population by adding the following further exclusions: (1) patients who entered the cohort prior to the release of the initial RECOVERY trial results; and (2) patients who initiated DEX use more than 1 day after the hospital admission date [see section *VII. SENSITIVITY ANALYSES, SA1, SA2*].
- Two sensitivity analyses will broaden the study population by loosening exclusions: (1) extend the lookback period to confirm a prior healthcare encounter to 365 days to allow for better capture of covariates among patients who do not have as frequent medical encounters (office visit or otherwise); and (2) allow patients with confirmed COVID-19 only after treatment index during the index hospitalization (no confirmation on/prior to treatment index or within 21 days prior to admission) [see section *VII. SENSITIVITY ANALYSES, SA3, SA4*].

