**VII. SENSITIVITY ANALYSES**

The following eight sensitivity analyses (SA1-SA8) in *Table 5* below were determined *a priori*. Additional sensitivity analyses may be considered *post hoc* upon review of preliminary results with the FDA RCA team. Unless otherwise specified, all sensitivity analyses will be applied in response to the primary objective but not the secondary objectives.

*Table 5: Summary of all sensitivity analyses planned a priori*

Category	Brief Description	Detail / Purpose
Inclusion/exclusion criteria (more specific)	SA1: Restrict study population to hospitalizations occurring after release of initial RECOVERY findings*	
Detail: Restrict cohort entry to on or after June 16, 2020, given the release of the RECOVERY results in early June 2020.
 
Purpose: Evaluate whether there is (qualitative) heterogeneity of the HR (which may be due to treatment pattern changes) after the substantial increase in DEX use in the US.

	SA2: Restrict study population to patients with immediate treatment initiation*	
Detail: Restrict DEX treatment index to DEX initiation on, or within 1d after, admission date.
 
Purpose: Evaluate whether there is (qualitative) heterogeneity of the HR (which may be due to covariate differences in patients treated earlier vs. later in the hospital stay) when restricting to DEX use upon admission, noting that the 1 day after admission was added to account for patients who may be admitted late in the evening who do not initiate treatment until the next morning.

Inclusion/exclusion criteria (more sensitive)	SA3: Broaden population to include patients with less frequent medical encounters*	
Detail: Lengthen baseline window to lookback 365 days to allow for better capture of covariates among patients who do not have as frequent medical encounters (office visit or otherwise). Evaluate whether covariate status using 183 day versus 365 day lookback is differential by treatment.
 
Purpose: Evaluate whether HR is robust within a broader cohort that may include people with less healthcare utilization (patients without a healthcare encounter within 183 days that do have one within 365 days prior to admission) prior to hospitalization for COVID-19. Determine if the lookback period impacts the distribution of baseline characteristics.

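### Section V.C.3 words SA2 as a whole-population exclusion, which conflicts with the Table 5 definition and, read literally, drops valid referents because of treatment after their index date

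*Protocol*

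**What the plan says.** Three parts of the protocol bear on SA2.

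- **V.C.3 Exclusion criteria.** SA1 and SA2 are introduced together: "Two sensitivity analyses will restrict the study population by adding the following further exclusions". The SA2 item is "2) patients who initiated DEX use more than 1 day after the hospital admission date". Nothing limits it to the DEX+ arm. The sentence refers the reader to section VII.
- **Section VII, Table 5, and Appendix B.** The short label is "Restrict study population to patients with immediate treatment initiation". The Detail line is "Restrict DEX treatment index to DEX initiation on, or within 1d after, admission date". Appendix B repeats both.
- **V.C.2 Treatment index, primary objective.** Each DEX user is matched to "at least 1 patient who has not (yet) used any CSI as of the DEX patient's index date". The referent's index date "will be defined by the index date of the matched users". The stated rationale is to draw "patients who have not initiated DEX from the risk set of patients who are eligible for initiating DEX at the same time".

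Under the initial-treatment approach in V.E, a referent who starts a corticosteroid after index stays in follow-up without censoring.

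**The concern.** Risk-set sampling is valid here because a referent qualifies on what is known at index and not on what happens later. A patient untreated on Day 1 who starts DEX on Day 4 is a proper referent for a DEX user indexed on Day 1. V.C.2 draws both groups from patients who have entered the cohort, so an exclusion at cohort level acts before sampling. Read that way, V.C.3 removes this patient on the strength of a Day 4 event.

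The protocol avoids this kind of conditioning elsewhere. Section VIII.A declines to account for treatment received after index, citing mediators and colliders. Exploration 3 declines to look forward when coding severity, citing immortal time.

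At stake is the interpretation of SA2. It is meant to show whether the hazard ratio differs, qualitatively, when DEX is started early. A shift produced by deleting referents could be mistaken for such a difference.

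**Working it through.** **1. The two versions, patient by patient.** The protocol states no figure to reproduce here, so the rules are set side by side. Take a DEX user indexed on Day 1 and the patients who might be matched to that user.

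| Patient | V.C.3 read literally | Table 5 Detail line |
|---|---|---|
| Starts DEX on Day 1 | kept as DEX+ | kept as DEX+ |
| Starts DEX on Day 4, as a DEX+ index case | removed | removed |
| Starts DEX on Day 4, as a Day 1 referent | **removed** | not removed |
| Starts methylprednisolone on Day 4, never DEX, as a Day 1 referent | kept | kept |
| Never receives a corticosteroid, as a Day 1 referent | kept | kept |

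The versions differ only in the third row. The literal rule is also uneven: a referent who later starts DEX goes, while one who later starts another corticosteroid stays.

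**2. How many patients could be touched.** The protocol does not give the share of referents who start DEX on Day 2 or later. V.C.2 says that more than 80% of DEX initiators started within 1 or 2 days, which does not isolate Day 2. Table A.2 gives days since hospitalization for DEX+ patients as 2 [2, 3]. Assume that the brackets are quartiles. If admission counts as day 1, at least about 25% of these DEX+ patients started on Day 2 or later; if it counts as day 0, at least about 75% did. That table comes from an earlier data cut and the DEX- comparison, and it describes DEX users, not referents. It shows only that late starters are not rare.

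**3. Direction of the bias (illustrative; every input is assumed).** DEX has no effect, so the true hazard ratio is 1. There are 150,000 patients per arm and 28 days of follow-up, discharge censors, and a Cox model with one covariate is fitted.

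- Frailty: f = exp(0.8Z − 0.32), with Z standard normal.
- Daily hazards: death 0.022·f; discharge 0.11/√f; later DEX start in referents h·f^γ, counted before day 20.
- γ = 0 makes late starting unrelated to prognosis; γ = 1 and γ = 2 make it moderately and strongly dependent on poor prognosis.
- Simplification: every referent who starts DEX after index is dropped, not only those starting on Day 2 or later.

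| h | γ | Referents starting later | Referent deaths: all → after dropping | HR, all kept | HR, later starters dropped |
|---|---|---|---|---|---|
| 0.01 | 0 | 5.9% | 15.4% → 15.3% | 1.004 | 0.959 |
| 0.01 | 1 | 6.1% | 15.6% → 14.9% | 0.997 | 0.982 |
| 0.01 | 2 | 8.5% | 15.4% → 13.6% | 1.007 | 1.053 |
| 0.025 | 0 | 13.6% | 15.5% → 15.3% | 1.014 | 0.898 |
| 0.025 | 1 | 13.4% | 15.6% → 14.1% | 1.002 | 0.970 |
| 0.025 | 2 | 16.0% | 15.4% → 12.3% | 1.009 | 1.089 |
| 0.06 | 0 | 27.5% | 15.6% → 15.3% | 0.993 | 0.756 |
| 0.06 | 1 | 25.5% | 15.5% → 12.7% | 0.986 | 0.924 |
| 0.06 | 2 | 26.3% | 15.4% → 10.9% | 1.009 | 1.118 |

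Keeping all referents recovers 1 to within simulation error: with about 150,000 × 0.155 = 23,250 deaths per arm, the standard error of the log hazard ratio is about √(2/23,250) = 0.009.

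Two forces oppose each other when later starters are dropped. They are known to have been alive and in hospital up to their start, so survival time leaves the referent arm and the hazard ratio falls (γ = 0). If they are also the sicker patients, deaths leave with them and the hazard ratio rises (γ = 2).

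**The case against.** The best case for the plan is that SA2 is defined correctly where it counts. V.C.3 defers to section VII, and the Detail line there and in Appendix B touches only the DEX treatment index. The referent rule in V.C.2 is nowhere changed for SA2. Elsewhere, including Exploration 4, patients who initiated DEX means the treated group, so the V.C.3 item can be read as DEX+ patients with a late index. The short label cannot be meant literally, since it would remove every never-treated referent and leave no comparison. Figure B.2 is not reproduced in the text at hand and may settle the matter. SA2 looks for qualitative heterogeneity, so a modest shift need not mislead.

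Most of this stands. A reader might infer from V.C.3 that SA2 will in fact delete later-starting referents. The documents do not support that: the operational line points the other way and is probably what is intended. Nor do they support any particular size of bias, because the simulation inputs are all assumed.

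The objection does not remove the conflict. SA1, in the same sentence of V.C.3, is a true whole-cohort exclusion, so reading SA2 in parallel is natural. V.C.3 is the only place that phrases SA2 as an explicit exclusion rule. The Detail line is silent on referents who start DEX later, so a programmer working from V.C.3 would find no instruction to keep them.

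**Conclusion.** The protocol describes one pre-specified sensitivity analysis in two ways that give different referent groups. The V.C.3 version, applied literally before risk-set sampling, conditions referents on treatment after index and would bias the SA2 hazard ratio. The Detail line does not have this problem, but leaves the handling of later-starting referents unstated.

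The direction of the bias depends on why referents start late. Its size cannot be derived from the documents; the simulated range of 0.76 to 1.12 under a true value of 1 is illustrative, and its extremes need roughly a quarter of referents to start later. The issue is confined to one of eight sensitivity analyses. It would be wrong to infer that the primary analysis is affected: its referent rule and follow-up are stated independently of SA2.

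**What to change.** Align item (2) in V.C.3 and the SA2 short label in Table 5 and Appendix B with the Detail line, and complete that line for referents. Suggested wording:

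*Restrict the DEX+ group (and their matched sets) to treatment index on Day 0 or Day 1. Referents are risk-set sampled as in the primary analysis from patients with no CSI as of that index date, and are not excluded for DEX or another CSI started after it.*

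The cost is a change of wording in three places, made before the inferential phase. No further data or analysis is needed.

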### D. Subgroups: COVID-19 severity at treatment index

The World Health Organization (WHO) Clinical Characterisation and Management Working Group proposed the WHO Clinical Progression Scale, which was created to classify COVID-19 patient outcomes according to disease progression and severity among ambulatory and hospitalized patients [*WHO Working Group 2020*]. We developed an adaptation of the scale that is a modified version of the WHO scale, referred to here as the mWHO score, to categorize

COVID-19 severity at treatment index among hospitalized patients. This mWHO score restricts to the WHO Scale categories specific to hospitalized COVID-19 patients (categories 4-9 in the original scale), which are then collapsed into three mutually exclusive categories based on supplemental oxygen and other ventilation support requirements (no oxygen, oxygen or NIV, IMV). The scale was operationalized by incorporating data from Day T-1 to Day T to account for the lag time in recording ventilation and oxygen supplementation data in the medical claims and chargemaster data. Patients will be assigned to one of the following mWHO categories based on the highest severity feature recorded from 1 day prior to treatment index to the treatment index date (*Day T-1 to Day T*):

- No oxygen at treatment index or within 1 day prior (No O2)
- Any oxygen or non-invasive ventilation with no record of invasive ventilation at treatment index or within 1 day prior (O2/NIV)
- Any use of invasive mechanical ventilation at treatment index or within 1 day prior (IMV)
- Composite of any O2/NIV or IMV at treatment index or within 1 day prior

Explorations were conducted to (1) determine the assessment period and justify the additional lookback to day T-1 for capture of the mWHO categories [see *Appendix A.3 Exploration 3*] and (2) justify the components of the mWHO algorithm definition [*Appendix A.4. Exploration 4*], respectively. The definitions of these severity categories included procedure codes (O2 and NIV procedure codes for O2/NIV; intubation, IMV, and extracorporeal membrane oxygenation [ECMO] procedure codes for IMV) and diagnoses indicating a clinical need for O2 (diagnosis of hypoxia or hypoxemia) or IMV (diagnosis of ARDS). While the primary algorithms used to define O2/NIV and IMV refer to both procedural and diagnostic encounters in the data, a sensitivity analysis was also added to evaluate the robustness of findings among the mWHO categories using an algorithm based on procedures alone [see section *VII. SENSITIVITY ANALYSES, SA7*].

Another COVID-19 severity score was developed by the FDA Sentinel Initiative to classify patients as asymptomatic/very mild, mild, moderate, severe, and critical [*Yih 2020*]. However, this score requires day-level diagnoses that are not always available via the HealthVerity inpatient chargemaster data (which is generally limited to diagnoses reported on the admission and discharge date). Therefore, use of this FDA Sentinel Initiative COVID-19 severity score is not feasible in this implementation.

Additional subgroups were added for patients who were in the intensive care unit upon treatment index and those who were not as a sensitivity analysis [see section *VII. SENSITIVITY ANALYSES, SA6*].

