### **Secondary Objective II -- New users of DEX (DEX+) versus new users of MPRED (MPRED):**

From the patients who enter the cohort, all patients who begin use of DEX or MPRED between the admission date (*Day 0*) and 1 day prior to discharge date (*Day D-1*) or a maximum period of 21 days after admission (*Day 21*). New use will be determined using a 90-day washout period to exclude patients with prior use of either DEX or MPRED during the 90 days prior. If a patient uses both treatments over the course of the admission, they will be assigned to their first qualifying treatment arm. If a patient receives both DEX and MPRED on the treatment index, they will be excluded since the effects or the drugs cannot be disentangled among these patients.

*Table 2: Risk set sampling (RSS) matching criteria*

RSS matching criteria	Variable type	Categories (for categorical) / calipers (for continuous)
Calendar date	continuous	±3 days
Age	continuous	±3 years
Sex	categorical	male, female
Combined comorbidity score over 183d baseline period [ Gagne 2011 ]	categorical	0-1, 2-3, 4-5, 6+
Time since hospital admission	categorical	0-1, 2-3, 4-5, 6 - 9, 10 - 14, 15 - 19, 20+ days
COVID-19 severity at treatment index date, per modified WHO (mWHO) score	categorical	No O2, O2/NIV, IMV (highest recorded from days T-1 to T) [see additional subgroup detail below in section V.D. Subgroups ]

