Baseline Covariates  (Day -183 to Day -1)	Baseline (pre-admission) comorbidities, co-medications, and health resource utilization.	
 
- Lifestyle factors: History of smoking/tobacco use*, Insurance type (commercial versus Medicare/Medicaid coverage)
 
- Comorbidities and comedICATIONS: asthma, hematological cancers, solid cancers, chronic lung disease, cardiovascular disease (any), diabetes, immunosuppressive conditions, kidney or liver disease, overweight, obesity (diagnosis in medical claims/chargemaster or body mass index <math>\geq 25</math>-<math><40</math> in EHR), severe obesity (diagnosis in medical claims/chargemaster or body mass index <math>\geq 40</math> in EHR), dependence on respiratory support, frailty score, neurological/cognitive impairment, 2+ or 3+ high-risk conditions (asthma, obesity, diabetes, chronic kidney disease, severe obesity, coronary artery disease, stroke, and chronic obstructive pulmonary disease), hypertension, statin use, steroid use (any, including inhaled), any immunosuppressant use, anticoagulant and/or antiplatelet use as well as the Combined comorbidity score [Gagne 2011]
 
- Health resource utilization: Number of days hospitalized, number of outpatient visits, number of pharmacy claims, number of distinct medications dispensed, any encounter indicating skilled nursing facility, influenza vaccination status
 

Pre-admission Covariates (Day -21 to Day -1)
 
AND
 
Pre-treatment Covariates (Day 0 to Day T, inclusive)
	
COVID-19 characteristics and treatments
	
 
- Pre-treatment COVID-19 status: dyspnea or hypoxia, pneumonia, ARDS, shock, non-respiratory organ failure, other organ support procedures (ECMO, KRT, Pressors), positive SARS-CoV-2 lab test result
 
- Pre-treatment medications including those that overlap with treatment index (Day T): Anticoagulant and/or antiplatelet agents, antibiotics, other experimental COVID-19 therapy listed in NIH guidelines (hydroxychloroquine/chloroquine, remdesivir, lopinavir/ritonavir and other HIV protease inhibitors, ivermectin, IL-6 inhibitors, IL-1 inhibitors, BTK inhibitors, JAK inhibitors, interferons, convalescent plasma, IVIG-SARS-CoV-2, Mesenchymal stem cells, COVID-19 mAbs [NIH 2020(b) as of the date of protocol finalization and may be updated as deemed necessary])
 

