
Pre-admission Covariates (Day -21 to Day -1)
	
COVID-19 symptoms and HCRU prior to the admission date.
	
 
- COVID-19 symptoms: pre-admission COVID-19 symptoms
 
- HCRU: Inpatient hospitalization, emergency room encounter
 

Admission Covariates (Day 0; CED)
	
Demographics, hospital facility characteristics, and COVID-19 severity on the admission date.
	
 
- Hospital and admitting characteristics: Hospital setting type, hospital teaching status, hospital number of beds, admission source, emergency room encounter, ambulance encounter, admission type
 
- COVID-19 severity at admission: mWHO severity categorization on the admission date
 

Pre-treatment Covariates (Day 0 to Day T, inclusive)
	
Treatments administered prior to or concurrent with treatment index date, pre-treatment clinical status, and time from admission to treatment.
	
 
- Pre-treatment COVID-19 status: Highest recorded mWHO severity
 
- Pre-treatment utilization characteristics: Number of days hospitalized, number of days with critical/ICU care, in ICU at treatment index, number of unique department codes, number of unique procedure codes
 
- Demographics: Month of treatment index, age, sex, insurance type, US region
 

*\*Smoking/tobacco use may be under-reported [see section VIII. Limitations for additional detail]*

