Summary of key findings:	
Additional detail related to the mWHO definition components are shown in Table A.4.
 
When mWHO categorization with additional clinical diagnoses [see Figure A.3, v3] was compared to mWHO categorization without additional clinical observations [see Figure A.3, v1], there were substantial shifts from the least severe category (no O2) to more severe categories (25-48% to O2/NIV and 1-2% to IMV) and from the O2/NIV to IMV category (4-6%). The shifts were differential according to treatment, as patients who initiated DEX had greater shifts and therefore differentially more misclassification/under-reporting of severity.
 
Figure A.4 and Figure A.5 are Venn diagrams illustrating the overlap and non-overlap of patients with corresponding encounters for the procedures, chargemaster diagnoses, and medical claim diagnoses for O2/NIV and IMV, respectively, to better visualize the percent of patients that would or would not be included if any of the encounter components were to be left out of the composite definitions used to define these subgroups. From these figures, we can conclude that the shifts from no O2 to O2/NIV were primarily driven by the inclusion of clinical diagnoses in the Chargemaster data and Medical Claims, e.g., the addition of hypoxia or hypoxemia diagnosis, as 47.6% of O2/NIV patients had Chargemaster or Medical Claims but did not have other procedure-based components [see Figure A.4]. Similarly, 4.9% of IMV patients had a diagnosis of ARDS via Chargemaster data or Medical Claims but did not have other procedure-based components [see Figure A.5].

Design decision:	Given the substantial shifts, especially from no O2 to O2/NIV, we incorporated both the procedure-based encounters and the diagnoses into our final algorithm.

Table A.4: mWHO definition components

mWHO Subgroup	Components used to define mWHO subgroups	Additional Details on Component definitions in HealthVerity data
No O2	Absence of evidence of a higher category	✓
O2/NIV	Standardized Procedure-related Diagnosis Codes	✓ - ICD-10 dx for O2/ventilation use
	Standardized Clinical Diagnosis Codes	✓ - ICD-10 dx hypoxia or hypoxemia
	Standardized Procedure Codes	✓ - HCPCS, CPT, Revenue Codes
	Free-text	✓ - Charge Codes
IMV	Standardized Procedure-related Diagnosis Codes	✓ - ICD-10 dx for intubation/IMV
	Standardized Clinical Diagnosis Codes	✓ - ICD-10 dx for ARDS

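### Non-invasive ventilation is never separated from plain oxygen in the match, the propensity score covariates or the balance table, so severity inside O2/NIV is controlled only through proxies

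*Protocol*

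**What the plan says.** Section V.D has the hospitalized WHO categories "collapsed into three mutually exclusive categories based on supplemental oxygen and other ventilation support requirements (no oxygen, oxygen or NIV, IMV"). The same grouping then recurs:

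- **Risk-set match (Table 2, section V.C.2):** "No O2, O2/NIV, IMV (highest recorded from days T-1 to T"). This applies to the CSI- and DEX- comparisons.
- **Candidate propensity score (PS) covariates (Table 3, section V.F):** "mWHO severity categorization on the admission date" and, for Day 0 to Day T, "Highest recorded mWHO severity".
- **Key subgroups (section III):** O2/NIV alone, and the O2/NIV/IMV composite.

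Table 3 also lists index-time clinical items: "dyspnea or hypoxia, pneumonia, ARDS, shock, non-respiratory organ failure, other organ support procedures (ECMO, KRT, Pressors"). It adds ICU days, ICU at index, and counts of department and procedure codes. None of these is NIV. Yet section V.D says that the algorithm draws on "O2 and NIV procedure codes for O2/NIV", so the NIV codes are already identified.

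Table 4, row 3 requires an ASD of at most 0.10 on all potential confounders. Section VI.A estimates the PS in the overall cohort, and section VI.B ties progression to the primary objective in the overall cohort.

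**The concern.** A patient on low-flow oxygen and a patient on NIV count as equally severe in the match and in both mWHO covariates. Matching on that score makes the O2/NIV level look balanced whatever mix of oxygen and NIV lies inside it. If clinicians choose dexamethasone partly on the intensity of respiratory support, some confounding by severity remains within the level, and no line of the balance table would show it directly.

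O2/NIV is a key subgroup and makes up most of the composite. In Table A.3 (an earlier data cut) the DEX+ counts are 592 oxygen and 62 IMV, so O2/NIV is 592/654 = 90.5% of those two groups. The level is also wide. Exploration 4 reports that 47.6% of its patients qualify through diagnoses alone, so it runs from coded hypoxia with no recorded procedure up to NIV.

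**Working it through.** The protocol states no bias figure, NIV share or NIV mortality ratio, so there is nothing to reproduce. The calculation below is an illustration.

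**Assumed inputs (not in the documents):** NIV share among O2/NIV patients p1 = 0.15 in DEX+ and p0 = 0.10 in referents; mortality ratio of NIV to oxygen R = 2 to 4.

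**From the documents:** ASD limit 0.10 (Table 4); oxygen stratum 592/1840 = 32.2% of DEX+ patients (Tables A.2 and A.3, earlier cut, taken as the O2/NIV share); RECOVERY rate ratio 0.82 in the oxygen stratum (section II.B).

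**1. Imbalance within O2/NIV.** ASD = |p1 - p0| / sqrt{[p1(1 - p1) + p0(1 - p0)]/2} = 0.05 / sqrt[(0.1275 + 0.0900)/2] = 0.152. This is above 0.10, but it is not computed if NIV is not a covariate.

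**2. Shift in the O2/NIV hazard ratio with no proxy adjustment.** Factor = [1 + p1(R - 1)] / [1 + p0(R - 1)], a risk-ratio approximation.

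| R | Factor | A true 0.82 reads |
|---|---|---|
| 2 | 1.15/1.10 = 1.045 | 0.86 |
| 3 | 1.30/1.20 = 1.083 | 0.89 |
| 4 | 1.45/1.30 = 1.115 | 0.91 |

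**3. Sensitivity to the assumptions.**
- Proxies remove half the imbalance (12.5% vs 10%): 1.125/1.10 = 1.023 to 1.375/1.30 = 1.058, so 0.82 reads 0.84 to 0.87.
- Smaller imbalance (12% vs 10%): 1.12/1.10 = 1.018 to 1.36/1.30 = 1.046. The ASD is 0.02/sqrt[(0.1056 + 0.0900)/2] = 0.064, which passes even within the subgroup.
- NIV commoner in referents (10% vs 15%): 1.10/1.15 = 0.957 to 1.30/1.45 = 0.897, so 0.82 reads 0.78 to 0.74.

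**4. Would an overall-cohort check catch it?** Assume that NIV is recorded only in O2/NIV patients. The overall shares are 0.322 × 0.15 = 4.8% and 0.322 × 0.10 = 3.2%. ASD = 0.0161 / sqrt[(0.0460 + 0.0312)/2] = 0.082, a pass. For share s, the ASD reaches 0.10 when 0.0025s = 0.01(0.125 - 0.01625s), that is s = 0.00125/0.0026625 = 0.47. Below about 47% O2/NIV, the overall check misses a within-level ASD of 0.15. In the composite (s = 0.905) the shares are 13.6% and 9.05%, and the ASD is 0.143, which would be flagged.

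**The case against.** A reader might infer that severity inside O2/NIV is neither adjusted nor visible. The protocol does not support that. ICU at index, ICU days, shock, non-respiratory organ failure, "other organ support procedures (ECMO, KRT, Pressors"), and procedure counts are all PS and balance candidates. Nothing confines them to ventilated patients, so they partly grade severity inside O2/NIV. SA6 also estimates the hazard ratio by ICU status. What remains is that these are proxies: ICU status cannot separate NIV from oxygen among patients in the same location, and hypoxia is itself a route into the O2/NIV level.

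A reader might also take Exploration 4 as evidence of direction, because it says that "patients who initiated DEX had greater shifts and therefore differentially more misclassification/under-reporting of severity". That sentence compares a procedure-only algorithm with one that adds diagnoses, and the protocol adopted the latter. It shows neither that DEX starters are sicker within the adopted category nor anything about NIV against oxygen.

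Three further defences have some weight:
- **Alignment with RECOVERY's categories (Exploration 4).** This justifies the subgroup, but it does not require confounder control to be equally coarse.
- **Flexibility.** Table 3 is a list for consideration, and HDPS or LASSO may be used. Neither guarantees that NIV enters the model.
- **Acknowledged residual confounding (section VIII.A).** This is true, but here one measured source can be reduced with codes already in use.

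**Conclusion.** The point holds in a limited form. NIV is not separated from oxygen in the match, the PS covariates or the balance table. Respiratory severity within O2/NIV is controlled only through proxies, and an NIV imbalance there is not directly visible. Size and direction are unknown from the documents. Under the assumed 15% vs 10% NIV and a mortality ratio of 2 to 4, the O2/NIV hazard ratio moves by a factor of 1.045 to 1.115 before proxy adjustment. It moves less after such adjustment, and the other way if referents have more NIV. The effect on the overall primary estimate would be diluted, because O2/NIV is only part of the cohort. This is an improvement worth making before the inferential phase, not an internal contradiction and not a reason to doubt the design as a whole.

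**What to change.** 1. Add one binary covariate, NIV procedure recorded Day T-1 to Day T, to Table 3 and to the PS model for each comparison.
2. Add it to the Table 4, row 3 balance list. Report its ASD in the overall cohort and also within the O2/NIV and composite subgroups, because the overall check alone can miss the imbalance.
3. Leave the O2/NIV subgroup as defined, so that comparability with RECOVERY is kept.

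The cost is one more PS parameter and a few lines in the balance report; the codes are already in the mWHO algorithm. The main limit is capture. With 47.6% of O2/NIV patients having no procedure component, a procedure-only flag will code some NIV users as non-users, and that error could itself differ by treatment. The covariate therefore reduces residual confounding but does not remove it, and the report should say so.
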